**LIST OF ABBREVIATIONS AND RELEVANT DEFINITIONS**

ABR	ABR form, General Assessment and Registration form, is the application form that is required for submission to the accredited Ethics Committee (In Dutch, ABR = Algemene Beoordeling en Registratie)
AE	Adverse Event
AR	Adverse Reaction
ASAT	Aspartate Aminotransferases
ALAT	Alanine Aminotransferases
BMI	Body Mass Index
CA	Competent Authority
CCMO	Central Committee on Research Involving Human Subjects; in Dutch: Centrale Commissie Mensgebonden Onderzoek
CRF	Clinical Research File
CRP	C-reactive Protein
CV	Curriculum Vitae
DTSQ	Diabetes Treatment Satisfaction Questionnaire
EQ-5D-5L	EuroQol 5 Dimensions 5 Levels questionnaire
GFR	Glomerular Filtration Rate
ESRD	End Stage Renal Disease
EU	European Union
FMD	Fasting Mimicking Diet
GCP	Good Clinical Practice
GRAS	General regarded as safe
HbA1c	Hemoglobin A1c
Hb	Hemoglobin
HDL	High Density Lipoprotein
HS	Heparan Sulfate
Ht	Hematocrit
IB	Investigator's Brochure
IC	Informed Consent
IGF-1	insulin-like growth factor 1
IL	Interleukin
IMP	Investigational Medicinal Product
IMPD	Investigational Medicinal Product Dossier
LDL	Low Density Lipoprotein

---

LED	Light-Emitting Diode
LUMC	Leiden University Medical Centre; in Dutch Leids Universitair Medisch Centrum
MCP-1	Monocyte Chemotactic Protein 1
METC	Medical research ethics committee (MREC); in Dutch: medisch ethische toetsing commissie (METC)
MHI	Microvascular Health Index
PBR	Perfused Boundary Region
RBC	Red Blood Cell
SAE	Serious Adverse Event
SDF	Sidestream Dark Field
SOD	Superoxide Dismutase
SPC	Summary of Product Characteristics (in Dutch: officiële productinformatie IB1-tekst)
Sponsor	The sponsor is the party that commissions the organisation or performance of the research, for example a pharmaceutical company, academic hospital, scientific organisation or investigator. A party that provides funding for a study but does not commission it is not regarded as the sponsor, but referred to as a subsidising party.
TNF-<math>\alpha</math>	Tumor necrosis factor-alpha
Wbp	Personal Data Protection Act (in Dutch: Wet Bescherming Persoonsgegevens)
WMO	Medical Research Involving Human Subjects Act (in Dutch: Wet Medisch-wetenschappelijk Onderzoek met Mensen)

## SUMMARY

**Rationale:** Micro- and macrovascular complications are the pathological hallmarks of diabetes mellitus, with diabetic nephropathy as one of the most serious microvascular complications. South Asians have a high incidence of type 2 diabetes and a higher chance to progress to end-stage renal disease than West European patients, which may be due to a higher sustained systemic and glomerular inflammation. The endothelial glycocalyx, covering endothelial cells, is essential for maintaining vascular homeostasis. In the diabetic environment, impairment of the glycocalyx can be induced by invading macrophages which excrete the glycocalyx degrading enzyme heparanase and its activator cathepsin L. In the glomerulus, impairment of the glycocalyx results in increased permeability for albumin alongside renal and vascular inflammation. SDF-imaging is a non-invasive technique to visualize the endothelial glycocalyx and obtains parameters that reflect the microvascular endothelial status, combined in the Microvascular Health Index (MHI). Here we investigate if dietary interventions, which either provide the nutritional building blocks to support and maintain the endothelial glycocalyx or reduce the overall inflammatory burden, can aid in restoration of the glomerular endothelial glycocalyx and in turn result in a reduction of albuminuria and further delay, or prevent renal damage.

**Objective:** The primary aim of the study is to improve microvascular endothelial health between baseline and 3 months expressed by the Microvascular Health Index, using a non-invasive imaging technique, upon two different dietary interventions compared to the placebo. The secondary objective is to monitor the dietary effects after 3 months on systemic inflammation, metabolic parameters and albuminuria. Finally, we aim to determine new urinary heparan sulfate fragment biomarkers which can be related to specific glomerular extracellular heparanase activity, a possible central player in local glomerular damage and renal inflammation.

**Study design:** A randomized, placebo controlled, 3-arm intervention field study for 3 months with additional 3 month follow up measurements.

**Study population:** Patients from South Asian descent in primary care medical centres in the The Hague area between 18 and 75 years old with type 2 diabetes mellitus and proven microalbuminuria.

**Intervention:** One group receives a monthly 5-day fasting mimicking diet, one group receives daily 4 capsules of a food supplement and one group receives daily 4 placebo capsules, all for 3 consecutive months.

**Main study parameters:** The primary endpoint is an improvement of the Microvascular Health index in the diet group compared to the placebo group and in the food supplement group compared to the placebo group, after 3 months of the intervention.

Secondary endpoints: reduce albuminuria, decrease inflammation (urinary heparanase and MCP-1 expression, serum CRP and MCP-1 levels), reduce occurrence of specific urinary HS domains, improve metabolic parameters; fasting glucose, HbA1c, C-peptide, IGF-1, total cholesterol, LDL cholesterol, HDL cholesterol, and triglycerides serum levels, waist circumference, waist-to-hip ratio, body weight and systolic blood pressure after 3 months of the fasting mimicking diet and after 3 months of the food supplement.

The legacy effect of the interventions is also determined, 3 months after stopping with the intervention.

**Nature and extent of the burden and risks associated with participation, benefit and group relatedness:** Eligible patients are randomly assigned to the fasting mimicking diet, food supplement or placebo arm. At baseline, after 3 months and at 6 months, the MHI is measured by non-invasive SDF imaging of the microcirculation under the tongue, and blood and urine samples are collected. In the FMD arm, dosages of the hypoglycemic drugs are adapted during the 5 days of the diet prevent hypoglycemia. Glucose monitoring is done during the diet and at the end of each month in all intervention arms through a finger prick blood sample.

## 1. INTRODUCTION AND RATIONALE

Micro- and macrovascular complications are the pathological hallmarks of diabetes mellitus. Diabetic nephropathy is one of the most serious microvascular complications associated with diabetes and the incidence of type 2 diabetes is rapidly increasing. Despite better regulation of hyperglycaemia and blood pressure, many patients still develop end-stage renal disease (ESRD).

To date, albuminuria is one of the first signs of microvascular dysfunction in the kidney and is an independent risk factor for disease progression. Changes in the endothelial glycocalyx function have shown to be important in the pathophysiology of glomerular diseases and development of albuminuria [1]. The glycocalyx is a carbohydrate-rich layer that covers the luminal surface of vascular endothelial cells. It consists of proteoglycans containing glycosaminoglycans, and incorporated plasma- and endothelium-derived glycoproteins, which together form a dynamic and interactive network at the vascular endothelial surface. The main glycosaminoglycan chains expressed in the glycocalyx are heparan sulfate (HS) and hyaluronan, which constitute 90% of the total amount [2].

[figure not shown]
The endothelial glycocalyx is essential for vascular homeostasis, it plays an important role in many vascular physiological processes such as mechanotransduction in response to shear stress [3], regulation of inflammatory and thrombotic responses [4] and providing selective permeability for circulating cells and proteins [5]. In the glomerulus, the glycocalyx covers the fenestrated endothelium and contributes to the glomerular filtration barrier [6]. Impairment of the glomerular glycocalyx leads to increased vascular permeability, which allows proteins such as albumin to pass through the fenestrated endothelium and enter into the subendothelial space [7, 8].

The endothelial glycocalyx is a dynamic network with a continuous balance between renewal, modification and degradation. This balance can be affected by mechanical as well as biochemical influences. Heparanase appears to be a crucial mediator in this process, as it is the only known mammalian enzyme that is capable of breaking down heparan sulfate [9, 10]. Activated heparanase has the ability to cleave heparan sulfate side chains, which results in modification of the glycocalyx. Under physiological circumstances heparanase activity is tightly regulated [11]. However, in glomerular diseases such as diabetic nephropathy, heparanase has been found to be released in renal tissue and urine [12-14]. Enhanced heparanase activity contributes to an imbalance in vascular glycocalyx function, with the diabetic environment being one of the strongest known inducers of heparanase activity. Circulating glycated serum proteins and inflammatory cytokines in diabetic patients

contribute to persistent activation of endothelial cells and attraction of monocytes. Diabetic nephropathy is characterized by glomerular inflammation with renal influx and accumulation of macrophages [15-17]. During sustained activation, endothelial cells are stimulated to produce proheparanase. This proheparanase can be turned into active heparanase in the extracellular environment, by the enzyme cathepsin L, which is secreted by local activated macrophages [11, 18]. Activated heparanase in turn can also activate macrophages through its toll-like receptors, creating a positive feedback loop [19].

In the South Asian population, the incidence of type 2 diabetes is very high [20-22]. These patients have a 40-fold higher chance to progress to end stage renal disease compared to West European diabetic patients [23]. This may be due to a higher systemic inflammation in these patients, which causes endothelial activation and induces glomerular inflammation [24-26]. Therefore, these high risk South Asian patients would benefit the most from early therapies that reduce systemic and glomerular inflammation and restore glycocalyx dimensions.

Diabetes is a systemic multi organ disease causing systemic microvascular complications and endothelial glycocalyx impairment. One way to investigate the endothelial glycocalyx is through sidestream darkfield (SDF) imaging. SDF imaging is a non-invasive technique that visualizes the sublingual microvasculature with a hand-held camera. This technique showed that red blood cells (RBCs) maintain a certain distance from the endothelium due to the presence of the glycocalyx. Damage to the glycocalyx allows RBCs to penetrate deeper towards the endothelial surface, which is expressed by an increased perfused boundary region (PBR) [27]. In previous studies, the PBR measured with SDF imaging was able to discriminate between different patient groups such as dialysis patients [28], lacunar stroke patients [29], critically ill patients [30], patients with ESRD [31], and patients with type 2 diabetes [32].

*Lee et al 2014, Deeper Penetration of Erythrocytes into the Endothelial Glycocalyx Is Associated with Impaired Microvascular Perfusion*

Other parameters however, give more insight into the quality of the microvascular perfusion, such as RBC filling percentage, capillary density and flow dependency [33].

Combining these parameters, Glycocheck BV developed the quantifiable Microvascular Health Index (MHI). The Microvascular Health Index ranges from 0.00 to 10.00 with a score between 0.00 – 1.00 reflecting a clinically perturbed glycocalyx and perfusion in the

microvasculature, a score between 1.00 – 2.00 a less than average health of the microvasculature, 2.00 – 3.00 an average microvascular health, between 3.00 and 5.00 an above average and a score above 5.00 a good functional microcirculation with adequate endothelial glycocalyx coverage and flow mediated adaptation.

In the last years, the endothelial glycocalyx has been targeted to ameliorate albuminuria in diabetic nephropathy. Therapeutics such as sulodexide and avosentan, intended to improve glycocalyx dimensions, failed to demonstrate albuminuria lowering effects or introduced limiting side effects in randomized controlled trials with diabetic patients [34-36].

However, new promising dietary interventions, that support endothelial glycocalyx function and reduce inflammation without introducing limiting side effects, are available.

Marine organism-derived fucosylated and sulfated polysaccharides that mimic glycosaminoglycans may have beneficial effects in diabetic patients by stabilizing the imbalanced glycocalyx. Fucoidan, extracted from brown seaweed, is one of those sulfated polysaccharides and is the main component of the food supplement Endocalyx™. Administration of the supplement in a mouse model of aging revealed beneficial vascular effects by reducing mesenteric macrophage accumulation and increasing capillary density. Moreover, daily administration of Endocalyx™ in healthy volunteers improved the quality of the endothelial glycocalyx, measured with SDF-imaging, compared to no treatment (unpublished data, [name]).

Simultaneously, the Longo group showed that a monthly cyclic 5-day periodic fasting mimicking diet (FMD) was able to rejuvenate the immune system, decrease tissue inflammation and extend life- and health span. In experimental studies, a fasting mimicking diet improved insulin sensitivity and reduced circulating inflammatory cytokines, which are involved in sustained activation of endothelial cells [37, 38]. Furthermore, two clinical trials revealed long lasting beneficial effects after 3 monthly FMD cycles on metabolic parameters (fasting glucose, systolic blood pressure and blood IGF-1 levels) and systemic inflammation in subjects with a high cardiovascular risk at baseline [38, 39].

This fasting mimicking diet may lead to beneficial effects in the diabetic kidney by several mechanisms. First, amelioration of glucose levels will decrease the amount of glycated serum proteins, which are one of the most potent inducers of heparanase. In addition, fasting induces upregulation of intra-glomerular autophagy [40]. Autophagy is a highly regulated lysosomal protein degradation pathway that removes protein aggregates and damaged or excess organelles to maintain intracellular homeostasis and cell integrity. Impairment in autophagy is thought to be involved in the pathophysiology of diabetic nephropathy and contributes to endothelial dysfunction [41-43]. Hyperglycaemia upregulates autophagy in several renal cell types such as mesangial cells, endothelial cells, and podocytes. However,

prolonged hyperglycaemia deprives autophagy, which is associated with increased severity of diabetic renal damage. [43] As autophagy is upregulated by fasting, the FMD may lead to a more balanced glomerular endothelium and removal of aggregated proteins or cell debris, which leads to a less pro-inflammatory milieu. This, in turn, causes less attraction of inflammatory cells, less activation of heparanase and thus less impairment of the glycocalyx. These dietary interventions, the Endocalyx™ food supplement and FMD, may be promising alternative interventions to support the imbalanced microvascular glycocalyx in diabetic patients by supplying glycocalyx substitutes and reducing glomerular inflammation.

## 2. OBJECTIVES

Primary Objective:

1. To investigate whether a fasting mimicking diet improves the Microvascular Health Index between baseline and 3 months in type 2 diabetic South Asian patients with microalbuminuria in comparison to the placebo group.
2. To investigate whether intervention with the food supplement Endocalyx™ improves the Microvascular Health Index between baseline and 3 months in type 2 diabetic South Asian patients with microalbuminuria in comparison to the placebo group.

Secondary Objectives:

If the fasting mimicking diet and the food supplement after 3 months can:

[figure not shown]
- Decrease inflammation (urinary heparanase and MCP-1 expression, serum CRP and MCP-1 levels).
- Reduce occurrence of specific urinary HS domains.
- Reduce albuminuria
- Improve metabolic parameters; fasting glucose, HbA1c, C-peptide, IGF-1, total cholesterol, LDL cholesterol, HDL cholesterol, and triglycerides serum levels, waist circumference, waist-to-hip ratio, body weight and systolic blood pressure.

### 3. STUDY DESIGN

A 6-month, single center randomized controlled trial to study the effects of dietary interventions on improving endothelial health in South Asian patients with diabetic nephropathy. In total 90 South Asian patients with type 2 diabetes and proven microalbuminuria between 18-75 years of age will be recruited at general practitioner centers in the The Hague region. Eligible patients will be included for a period of 6 months. Patients will be randomly assigned to receive the fasting mimicking diet, food supplement or placebo for a period of 3 months. The primary endpoint is an improvement of the Microvascular Health index after 3 months in the diet group compared to the placebo group and in the food supplement group compared to the placebo group, measured with SDF-imaging. After 6 months, which is 3 months after stopping with the interventions, patients will also return for a follow-up measurement to investigate possible legacy effects of each intervention.

The food supplement and placebo arm will be double blinded. The placebo arm will also be used as a control group for the FMD arm.

Study procedures will take place at the practice of the general practitioner and will be performed by LUMC research staff. The general practitioner will not perform any of the study procedures. Flow chart I gives an overview of the study design and time points for study visits.

Flow chart I

#### 4. STUDY POPULATION

##### 4.1 Population (base)

The study population consists of South Asian patients with type 2 diabetes and microalbuminuria between 18-75 years old. In total 90 patients will be included in the study.

##### 4.2 Inclusion criteria

In order to be eligible to participate in this study, the following criteria must be met:

1. South Asian patient with diabetes mellitus type 2.
2. Female or male, aged between 18 and 75 years.
3. Body Mass Index  $\geq 18.5$ .
4. CKD-EPI  $>45 \text{ ml/min}/1.73\text{m}^2$ .
5. Proven microalbuminuria defined as albumin/creatinine ratio  $\geq 0.3$  and  $<30 \text{ mg}/\text{mmol}$  (single portion) or 3-300 mg albumin per day (24 hours urine collection) in the last twelve months.
6. Systolic blood pressure  $\leq 180 \text{ mmHg}$ .
7. Treatment with hypoglycemic drugs: metformin, sulphonylureas and/or insulin.
8. Subject is willing to participate in the study, must be able to give informed consent and the consent must be obtained prior to any study procedure.
9. Patients must be able to adhere to the study visit schedule and protocol requirements.
10. If female and of child-bearing age, patients must be non-pregnant, non-breastfeeding, and use adequate contraception.

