#### **4.4 Sample size calculation**

The primary outcome will be improvement of the Microvascular Health Index after 3 months. The sample size is chosen according to a pilot study with 13 healthy volunteers receiving the food supplement Endocalyx™ for 3 consecutive months. After 3 months, a 31% improvement in Microvascular Health Index was demonstrated, expressed in a significant increase of the MHI from 1.05 at baseline, to 1.38 at 3 months (improvement of 0.33).

Group sample sizes of 23 per group achieve 80% power to detect a difference of 0.35 between the null hypothesis that group improvement means are 0.0 and the alternative hypothesis that the improvement mean of group 2 or 3 is 0.35 with estimated group standard deviations of 0.41 with a significance level (alpha) of 0.05000 using a two-sided two-sample t-test. If we anticipate a 25% drop out rate per group, we will need 30 patients per group.

Therefore, we decided to enrol a total number of 90 patients in this study.

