#### 7.1.2 Secondary study parameters/endpoints

Secondary endpoints include;

- Albuminuria: urinary excretion of albumin, using albumin/creatinine ratio in mg/mmol.
- Inflammation: urinary heparanase and MCP-1 expression, serum C-reactive protein, and MCP-1 levels.
- Metabolic response: fasting glucose, HbA1c, C-peptide, IGF-1, total cholesterol, LDL cholesterol, HDL cholesterol, triglycerides levels, body weight, waist circumference, waist-to-hip ratio and systolic blood pressure.
- Identifying specific urinary heparan sulfate domains.

To evaluate the legacy effects of the interventions, the primary and secondary parameters will also be assed three months after stopping the intervention.

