### 9.2 Secondary study parameters

The categorical data will be summarized by the frequencies and percentages and tested within the group between baseline and 3 months using a Pearson's Chi-squared test. The continuous data will be summarized in mean with standard deviation in case of normal distribution or median with interquartile range in case of non-normal distribution. A paired two-tailed Student's t test or Wilcoxon signed rank test will be used to calculate the effect within the group between baseline and 3 months.

Differences in outcomes between the groups (diet vs placebo and supplement vs placebo) will be tested with a Student's t test for normally distributed data or Mann-Whitney *U* test for non-normally distributed data.

A paired two-tailed Student's t test or Wilcoxon signed rank test for differences of the primary and secondary parameters between baseline and 6 months within the group will be used to evaluate the legacy effect of the interventions 3 months after stopping with the intervention.

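### Albumin/creatinine ratio is admitted over a 100-fold range but analysed in mg/mmol with no log scale or baseline adjustment, which costs power on the albuminuria endpoint

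*Combined protocol and SAP*

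**What the plan says.** Criterion 5 in section 4.2 opens with "Proven microalbuminuria defined as albumin/creatinine ratio" and gives limits of 0.3 (inclusive) to below 30 mg/mmol on a single urine portion. The alternative route is "3-300 mg albumin per day (24 hours urine collection) in the last twelve months". One qualifying result within the year is enough. No repeat sample and no ACR threshold at the baseline visit is required.

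Elsewhere the population is named without numbers. Section 4.1 says "The study population consists of South Asian patients with type 2 diabetes and microalbuminuria between 18-75 years old", and section 3 plans to recruit "South Asian patients with type 2 diabetes and proven microalbuminuria between 18-75 years of age". Both primary objectives in section 2 are stated for patients with microalbuminuria.

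The secondary endpoint in section 7.1.2 is "Albuminuria: urinary excretion of albumin, using albumin/creatinine ratio in mg/mmol". For differences between arms, section 9.2 plans a "Student's t test for normally distributed data or Mann-Whitney *U* test for non-normally distributed data". It does not say whether the 3-month value or the change from baseline is tested. It mentions no transformation and no adjustment for baseline.

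The sample size rests on a different variable: "The primary outcome will be improvement of the Microvascular Health Index after 3 months" (section 4.4).

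**The concern.** If an intervention lowers albumin excretion by roughly the same proportion in everyone, the fall in mg/mmol is proportional to where the patient started. Over a 100-fold entry range, the absolute changes then differ 100-fold between patients who responded equally well. A comparison in mg/mmol gives most of its weight to the few patients with high values and treats the rest as near zero. Chance variation in those high values swamps the effect.

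Reducing albuminuria is the clinical rationale for the trial, so this is the secondary endpoint readers will look at first. With about 23 completers per arm, a null result from an inefficient analysis would be hard to interpret. It could mean no effect, or an effect that the chosen scale could not show.

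There is also a matter of description. Conclusions will be stated for patients with microalbuminuria, and criterion 5 is the only numerical content behind that term.

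**Working it through.** **The plan's own figure.** Section 4.4 states that "Group sample sizes of 23 per group achieve 80% power to detect a difference of 0.35", with SD 0.41 and two-sided alpha 0.05. A two-sample t-test calculation gives n = 22.54, so 23 per group, with power 80.8% at 23. The figure reproduces. It concerns the Microvascular Health Index (MHI) only and uses no ACR input. No power is stated for albuminuria.

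**Width of the entry range** (limits from section 4.2).
- Spot urine: 30/0.3 = 100.
- 24-hour urine: 300/3 = 100.
- Agreement of the two routes: 3/0.3 = 10 and 300/30 = 10, so both ends imply the same 10 mmol creatinine per day.

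**What the range does on the mg/mmol scale.** The documents give no expected effect, so a 30% relative fall is assumed for illustration.
- Entry at 0.3: 0.30 × 0.3 = 0.09 mg/mmol. The largest possible fall is 0.3.
- Entry near 30: 0.30 × 30 = 9 mg/mmol.
- If baselines are spread evenly on the log scale, ln(10)/ln(100) = 50% of patients lie below 3 mg/mmol. With an equal relative fall, those above 3 supply (30 − 3)/(30 − 0.3) = 27/29.7 = 91% of the average absolute fall. The other half supply 9%.

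**Power by simulation.** Assumptions, none of them given in the documents except the limits and the 23 per arm:
- The patient's underlying ln(ACR), u, is uniform between ln 0.3 and ln 30.
- Baseline ln(ACR) = u + e0. At 3 months, ln(ACR) = u + e1 on placebo and u + ln(0.7) + e1 on active, where ln(0.7) = −0.357.
- e0 and e1 are normal with equal variance, and the SD of e1 − e0 (the log-change SD) is 0.3, 0.5 or 0.7.
- 23 per arm, two-sided 5% level.

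| Between-arm analysis | SD 0.3 | SD 0.5 | SD 0.7 |
|---|---|---|---|
| t test, change in mg/mmol | 58% | 27% | 16% |
| Mann-Whitney, change in mg/mmol | 81% | 43% | 26% |
| log(ACR) at 3 months, adjusted for baseline log(ACR) | 97% | 65% | 42% |

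Simulation error is about one percentage point. If section 9.2 is read as comparing 3-month values without baseline, power at SD 0.5 is only 11 to 13% with either test.

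**Check by formula.** At SD 0.5 the standardised effect on the log scale is 0.357/0.5 = 0.71. A two-sample t test on log change with 23 per arm then has 66% power, in line with the simulated 65%.

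**Is the cause the range or the scale?** In a variant with all the within-person variation placed at 3 months (SD 0.5), the full range was compared with a range one tenth as wide. The narrower range is for comparison only.

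| Analysis | 100-fold range | 10-fold range |
|---|---|---|
| t test, absolute change | 31% | 48% |
| Mann-Whitney, absolute change | 46% | 54% |
| t test, log change | 66% | 66% |

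The wide range costs power only on the mg/mmol scale. On the log scale its width does not matter.

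**The case against.** **Rank tests already deal with skew.** Section 9.2 allows medians and Mann-Whitney for non-normal data, so a few large changes need not dominate. This stands in part. Mann-Whitney on change is clearly better than the t test, and with a log-change SD of 0.3 it reaches 81%. It still ranks absolute changes, so patients with low baselines crowd around zero whatever their relative response, and it makes no use of baseline. It stays 16 to 22 points below the adjusted log analysis across the table.

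**The endpoint is secondary and unpowered.** True. The primary endpoint is the MHI, and nothing here touches it. That limits the weight of the point, but the improvement uses data already being collected.

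**The figures rest on assumptions.** Also true. The documents give no ACR distribution, effect size or within-person SD. If the intervention acted by a fixed number of mg/mmol rather than a proportion, the log scale would lose its advantage. But a fixed fall cannot exceed 0.3 mg/mmol in a patient who enters at 0.3.

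**A stronger reading that a reader might draw.** The lower limits of 0.3 mg/mmol and 3 mg/day might be taken for a decimal slip that admits patients without microalbuminuria. The documents do not support that. They give no other cut-off, normal range or source, so by the protocol's own definition everyone enrolled has microalbuminuria. Calling the limits too low requires a figure from outside. The two routes also agree with each other, which makes a misprint in only one of them unlikely, although it cannot show that both were intended. The rationale in section 1 speaks of early therapies, so a low threshold could be deliberate, but the protocol does not say so.

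**Conclusion.** The point holds as a matter of analysis. A 100-fold entry range is combined with an absolute scale and no baseline adjustment, and under the assumptions shown this costs a substantial share of the power available for albuminuria. Power is about 16-58% for the t test on change and 26-81% for Mann-Whitney on change, against 42-97% for the adjusted log analysis. These figures depend on log-uniform baselines, a 30% relative fall and a log-change SD of 0.3 to 0.7. The direction follows from the limits in section 4.2 whenever effects are roughly proportional.

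On the population, the documents show only that the range is wide and unexplained. They do not show misclassified patients, and the share of patients near the lower limit is unknown.

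The effect is confined to one secondary endpoint and to how the population is described. The MHI analysis and its 23 per group do not change.

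**What to change.** 1. In section 9.2, specify for albuminuria a linear model of log(ACR) at 3 months on treatment arm, with baseline log(ACR) as covariate. Report each active arm against placebo as a ratio of geometric means with 95% CI. State how values below the assay's detection limit are handled, since the log needs a positive value.
2. Do not put a baseline-by-arm interaction in the main analysis. With about 23 completers per arm it would be estimated imprecisely. If wanted, label it exploratory.
3. In the conclusions, give the enrolled ACR range (0.3 to below 30 mg/mmol) beside the term microalbuminuria, and tabulate baseline ACR by arm.
4. Have the sponsor confirm that both lower limits in criterion 5 are intended and add the reason or source. No replacement limit is proposed here.

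Items 1 to 3 need a few lines of text and no extra data, visits or patients: urinary albumin and creatinine are already measured at the study visits, and SPSS fits the model. The one trade-off is that results appear as ratios rather than differences in mg/mmol. Medians by arm in mg/mmol can be shown alongside. Item 4 is a query to the sponsor.
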